In order to fully assess the utility of dynamic PET imaging, an understanding of the test-retest repeatability of dynamic imaging is necessary. Generally, the standardized uptake value (SUV), a semi-quantitative measure of PET radiotracer uptake, has been shown to be a highly repeatable imaging biomarker (6). In recurrent ovarian cancer patients, one study found FDG uptake measurements to have repeatability coefficients of 16.3% and 17.3% for SUVmean and SUVmax, respectively (7). Using a mouse model, Whisenant et al found kinetic parameters extracted from dynamic PET images were sufficiently repeatable to be used for therapy response assessment (8). While several human studies have indicated PET metrics extracted from dynamic PET images also show a high degree of test-retest reliability, a complete evaluation of dynamic PET repeatability remains incomplete (9, 10, 11).

Since PET/CT imaging (dynamic or static) is performed over an extended period of time, patient motion (particularly respiratory motion) is inevitable and can cause significant image artifacts (12). Volume and SUVmax (vital metrics in PET/CT imaging) have been shown to be significantly impacted by movement during imaging. Motion has been shown to cause an underestimation of SUVmax by as much as 28% and an overestimation of volume by up to 130% (13). Different methods have been developed to manage the respiratory motion problem including breathhold procedures (14), respiratory gating (15), and other post-processing techniques (16). Respiratory gating involves sorting the PET data into different bins with respect to the respiratory status. Each bin thus contains only a part of total motion and will have reduced motion artifacts. Unfortunately, the bins contain only a part of the total number of events detected in the scanner, which leads to more noise. OncoFreeze is a novel approach to PET motion correction that utilizes 100% of events, which are corrected to an optimal gate image utilizing

an optical flow algorithm, creating the potential for motion corrected images without increasing image noise.

II. Objectives

1. Assess the technical feasibility of dynamic, whole-body multiparametric PET imaging
2. Assess the quantitative and clinical impacts of a novel approach to PET data motion correction (OncoFreeze), relative to more conventional static and respiratory-gated PET images.
3. Quantify the test-retest repeatability of quantitative metrics extracted from dynamic PET images.
4. Comparison of the early and late Patlak images to determine the optimal post-injection time period for dynamic PET imaging for Patlak analysis.

III. Eligibility

Main Cohort: Any patient 18 years of age or older, scheduled to undergo a clinical PET/CT scan with any clinically prescribed radiotracer* for known or suspected malignancy (pathologic confirmation not required), and able to provide informed consent is eligible to participate in this study.

Repeatability Cohort: Any patient 18 years of age or older, scheduled to undergo a clinical PET/CT scan with FDG or ⁶⁸Ga- DOTA-0-Tyr3-Octreotide (DOTATATE) for known or suspected malignancy (pathologic confirmation not required), and able to provide informed consent is eligible to participate in this study.

***NOTE:** Some patients are evaluated clinically with multiple radiotracers prior to therapy. Patients scheduled to undergo multiple PET/CT imaging procedures will be eligible to have dynamic imaging performed during each of these procedures. However, these patients would only be eligible to have 1 repeat imaging procedure for research purposes.

IV. Patient Registration

Patients must not start any protocol intervention prior to registration through the Siteman Cancer Center.

The following steps must be taken before registering patients to this study:

1. Confirmation of patient eligibility
2. Registration of patient in the Siteman Cancer Center database
3. Assignment of unique patient number (UPN)

Confirmation of Patient Eligibility

Confirm patient eligibility by collecting the information listed below:

1. Registering MD's name
2. Patient's race, sex, and DOB
3. Three letters (or two letters and a dash) for the patient's initials
4. Copy of signed consent form
5. Completed eligibility checklist, signed and dated by a member of the study team
6. Copy of appropriate source documentation confirming patient eligibility

Patient Registration in the Siteman Cancer Center Database

All patients must be registered through the Siteman Cancer Center database.

Assignment of UPN

Each patient will be identified with a unique patient number (UPN) for this study. All data will be recorded with this identification number on the appropriate CRFs.

V. Patient Compensation

Patients will be compensated for their participation in this study. Upon successful completion of the study, patients will be paid \$50.00 and given a parking voucher, if necessary, for research imaging performed on the day of their clinical scan. Patients who participate in a retest imaging session will be paid an additional \$150.00, as well as a parking voucher, if they drove to campus.

VI. Methods

Main and Repeatability Cohorts

This protocol seeks to evaluate: (1) Metrics derived from dynamic positron emission tomography / computed tomography (PET/CT) imaging, (2) methods for achieving motion correction of PET/CT images, and (3) the repeatability of dynamic imaging. Clinical PET/CT imaging is normally performed by injecting a patient with a radiopharmaceutical (most commonly FDG) and collecting images using a PET scanner (preceded by a brief CT scan) after an uptake phase, which varies in duration depending on radiotracer. The data for this study will mostly be collected by asking patients to have PET images collected during the uptake phase (preceded by a low-dose research CT scan) in addition to the normal clinical images. We will also ask them to remain in the scanner for up to 20 minutes following the clinical scan in order to perform additional research PET imaging. The normal clinical scan (including radiation dose) will not be impacted by this study. However, the low-dose CT performed prior to the dynamic imaging will result in additional radiation exposure. All scans will be performed on a Siemens Vision scanner.

Ideally, participants will be positioned in the same way they'll be positioned for their clinical scan. However, as the research imaging takes a considerable amount of time, patients may be positioned differently (e.g. with arms by their sides) if the clinically-indicated position would prove too difficult.

Repeatability Cohort Only

A subset of patients (up to 30 scheduled to undergo FDG or DOTATATE PET/CT imaging) will be asked to return to the CCIR within 7 days for a repeat imaging study. This time-point will involve the same procedures performed during the initial imaging visit.

Study Procedures

Following the consent process, patients will be escorted to the PET/CT imaging suite where they will be positioned on the imaging bed. As part of the routine clinical PET/CT procedure, an IV will be placed. A low-dose CT will then be performed, followed by the administration of the [clinically-prescribed] radiotracer. Immediately following the tracer administration, PET imaging will begin and continue for approximately 40 - 60 minutes at which point the clinical PET/CT procedure will be performed. Patients will be asked to use the bathroom between the research and clinical imaging.

Specific Dynamic Imaging Procedure

- 1) Upon arrival, patients will be taken to a preparation room where they will be kept warm and they will have time to review the consent form and ask any questions they might have about the dynamic imaging study.
- 2) Patients will be asked to void immediately prior to the start of PET/CT imaging.
- 3) Patients will then be escorted to the scanner and have one IV placed.
- 4) A low-dose CT will be performed.
- 5) A single weight-based dose of a radiotracer will be administered.
- 6) Patients should be positioned comfortably so as to reduce the likelihood of movement during the scan.
- 7) Dynamic PET/CT imaging (utilizing multiple whole-body passes) will begin immediately following the radiotracer injection and will continue until approximately 10 – 20 minutes prior to the start of the clinical scan. These passes will be used to generate early Patlak images.
- 8) Upon completion of the dynamic scan, patients will be asked to use the bathroom to empty their bladders, and then the clinical scan procedure will begin.
- 9) During the clinical scan procedure, patients will wear an Anzai belt, a device that tracks respiratory motion.
- 10) Following the clinical imaging, patients will remain in the scanner for approximately 20 minutes while additional research PET images are

collected. These additional passes will enable the generation of late Patlak images for comparison with early Patlak images.

Repeat Dynamic Imaging

Patients who agree to participate in the repeatability sub-study will be asked to return to the CCIR within 7 days for an additional imaging study. This visit will involve the same procedures as the initial imaging visit and will be performed entirely for research purposes. The repeat visit should include approximately the same radiotracer and CT doses. In the case of imaging delays (i.e. an uptake time differing significantly from what is clinically recommended) during the initial imaging visit, the same delay should be incorporated into the repeat imaging visit.

VII. Data Analysis

The primary endpoint of this prospective study is the feasibility of multiparametric PET in a general oncology population. A total of 75 subjects will be recruited for the multiparametric PET portion of the study. If we observe a successful completion rate of 81.3% (i.e., 61 of 75 subjects), the exact 95% confidence interval for that proportion and sample size would be 71-89%. The lower limit of this confidence interval will effectively indicate that the true successful completion rate is highly likely to be $\geq 70\%$ and that multiparametric PET is feasible in a general oncology population.

Primary aim: The feasibility of rapid, whole-body dynamic PET imaging will be assessed by evaluating the practicality of acquiring dynamic PET data in the clinic. The feasibility of multiparametric PET for oncologic imaging will be defined as successful completion of the study imaging component in at least 70% of cases. Successful completion of the study imaging component will be defined as: (1) patient remains on scanner for the full dynamic phase of PET imaging prior to the standard-of-care PET/CT and (2) automated scanner software is able to successfully generate valid parametric maps (requires at least three consecutive whole-body PET acquisitions without substantial motion between acquisitions). Feasibility is important to establish due to the added demands on patients arising from the long imaging period. In addition, novel quantitative metrics derived from dynamic PET acquisitions will be compared with standard semiquantitative metrics, such as SUV and metabolic tumor volume (MTV), obtained from the clinical PET/CT scan.

Secondary aim #1: The quantitative and clinical impacts of OncoFreeze (specifically, on semi-quantitative SUV metrics and on the number of detectable lesions) will be assessed by comparing motion-corrected images derived from OncoFreeze with standard static non-gated PET images and conventionally gated PET images. Two independent readers blinded to the

reconstruction approach will score image quality utilizing a standard Likert-type scale and will extract quantitative metrics (e.g., SUV-max, SUV-peak) for any apparent FDG-avid lesions. Results will be compared for (1) motion-corrected images derived from OncoFreeze, (2) standard static non-gated PET images, and (3) conventionally gated PET images.

Secondary aim #2: The repeatability of dynamic imaging will be evaluated by calculating the measurement agreement and relative differences in semi-quantitative PET metrics between test and retest dynamic images. Imaging metric agreement will be measured using Bland-Altman analysis. Groupwise differences between imaging time-points will also be assessed using t-tests or Mann-Whitney U tests, depending on normality.

Secondary aim #3: The early and late Patlak images (specifically: metabolic rate [slope] and volume of distribution [intercept] images) will be compared in a head-to-head fashion, both qualitatively and quantitatively. This aim will help to determine the optimal post-injection time period for dynamic PET imaging for Patlak analysis.

VIII. Study Risks and Benefits

1) IV Risks:

The risks from IV placement include bruising, pain, or infection at the injection site and possible leaking of IV fluid into nearby tissues. The risk of infection is quite low. There is a moderate risk of pain or bruising. Intravenous injections will be performed only by experienced staff and a physician will be available throughout the procedure in case of any infusion side effects.

2) FDG Risks:

FDG is FDA-approved and known to be very safe. There are few known side-effects associated with FDG. In a large cohort, less than 1% or less of patients experienced transient hypotension, hypo- or hyperglycemia, or transient increases in alkaline phosphatase. The package insert for FDG lists no warnings, interactions, or precautions. A review of the literature reveals no adverse effects.

3) DOTATATE Risks:

Risks associated with DOTATATE were assessed in 3 clinical trials and no serious adverse events were reported. In a small percentage of patients, nausea and/or vomiting have been reported following the administration of DOTATATE.

4) Radiation Risks:

This research involves exposure to radiation from PET/CT imaging. As part of the repeatability cohort, patients will receive 1 radiotracer dose (either FDG or DOTATATE) and 3 low-dose CTs as part of the research procedures. The risk from the radiation exposure in this study is too small to be measured. It is not a big risk when compared with other risks you take every day. For more information about radiation exposure, please see the "Radiation Fact Sheet" at <https://hrpo.wustl.edu/participants/radiation-fact-sheet>.

5) PET/CT Imaging Risks:

Patients may experience some discomfort having to lie still for an extended period of time. Patients who dislike small spaces may also find the PET/CT scanner uncomfortable.

IX. Regulatory and Reporting Requirements

The Principal Investigator is responsible for ensuring the safety of subjects who have enrolled in the study. The PI will monitor the study for adverse events directly attributable to participation in this study (i.e. events associated with the additional research PET/CT imaging, not events associated with the clinical PET/CT imaging, including radiopharmaceutical administration). If any breach of confidentiality were to occur, it would be reported according to the HRPO-recommended guidelines.

Reporting

Based on the half-lives of the tracers involved in this study, adverse event tracking will be performed for 24 hours starting at the time of radiotracer administration. Any reported events, anticipated or unanticipated, will be reviewed by the PI and reported per the WUSTL HRPO guidelines. These events will be followed until resolution.

Study deviations will be tracked and recorded throughout the study. Any serious deviations will be reported immediately to the IRB. Otherwise, study deviations will be reviewed by the PI and reported on an annual basis.

X. Data and Safety Monitoring Plan

The principal investigator will review all patient data at least every six months, and provide an annual report to the QASM Committee. This report will include

1. the protocol title, IRB protocol number, and the activation date of the study.
2. the number of patients enrolled to date
3. the date of first and most recent

patient enrollment 4. a summary of all adverse events regardless of grade and attribution 5. a response evaluation for evaluable patients 6. a summary of any recent literature that may affect the ethics of the study. The study principal investigator and clinical research associate will monitor for serious toxicities on an ongoing basis. Once the principal investigator or clinical research associate becomes aware of a serious adverse event, the SAE will be reported to the HRPO and QASM Committee [add other reporting requirements here if applicable, e.g. sponsor, FDA, collaborating institutions] within 10 working days.

Adverse Events

For the purposes of this protocol, an adverse event (AE) is any untoward medical occurrence within 24 hours of radiotracer administration (e.g., sign, symptom, disease, syndrome, intercurrent illness, abnormal laboratory finding) that emerges or worsens relative to pre-imaging baseline. The Investigators will monitor the occurrence of adverse events during the course of the study. The Investigators need to assess whether there is a reasonable possibility that the study imaging agent caused or contributed to an AE using the following criteria as a guide:

Definite: The adverse event is clearly related to the imaging procedure.

Probable: There is a clinically plausible time sequence between the onset of the AE and administration of imaging tracer. The AE is unlikely to be caused by the concurrent/underlying illness, other drugs, or procedures.

Possible: There is a clinically plausible time sequence between the onset of the AE and administration of imaging tracer, but the AE could also be attributed to the concurrent/underlying disease, other drugs, or procedures.

“Possibly” should be used when the administration of the study imaging tracer is one of several biologically plausible causes of the AE.

Unlikely: The adverse event is doubtfully related to the imaging procedure.

- Not Related: Another cause of the AE is the most plausible and/or a clinically plausible temporal sequence is inconsistent with the onset of the AE and the imaging procedure; and/or a causal relationship is considered biologically implausible.

If any adverse event is considered to be definitely, possibly or probably related to the investigational imaging tracer, that event will be followed until resolution or until it is deemed chronic or irreversible by the Investigator. If an event is unlikely or not related to the investigational imaging tracer, the event will not be reported.

All adverse effects will be documented and recorded in the medical record and will include:

- Specific reaction according to NCI Common Toxicity Criteria, version 4.0.
- Duration of the reaction
- Severity/grade according to NCI Common Toxicity Criteria, version 4.0. If the adverse event is not addressed by the Common Toxicity Criteria, the severity should be rated as mild (grade 1), moderate (grade 2), severe (grade 3), or life threatening (grade 4).
- Relation of reaction to study agent
- Management of reaction, including any interruption or dose modification of the study drugs.

Event Types

The term “adverse event” is defined in the International Conference on Harmonization Guideline for Good Clinical Practice as follows:

“Any untoward medical occurrence in a patient or clinical investigation subject administered a pharmaceutical product and which does not necessarily have a causal relationship with this treatment. An adverse event (AE) can therefore be any unfavorable and unintended sign (including an abnormal laboratory finding), symptom, or disease temporally associated with the use of a medicinal (investigational) product whether or not related to the medicinal (investigational) product”.

Medical conditions of a subject that exist prior to receiving the investigational imaging tracer will be recorded as medical history. After administration of the investigational imaging tracer, all new medical conditions are considered adverse events. Adverse events occurring in this trial will be recorded in data collection forms, regardless of whether or not they are thought to be associated with the investigational imaging tracer throughout the study period (From the time of consent until the completion of the repeat PET/MR scan). However, the Investigator also will assess the possible relationship between the adverse event and the investigational imaging tracer.

Serious Adverse Events

Any adverse drug experience, occurring at any dose that results in any of the following:

- Death

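### The $50 is worded as conditional on completing the study, while the primary endpoint is a completion rate, so the payment could favour the patient-dependent part of that endpoint

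*Combined protocol and SAP*

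**What the plan says.** **Payment (Section V, Patient Compensation).** The section opens in general terms: "Patients will be compensated for their participation in this study". The sentence that sets the condition for the initial visit is narrower: "Upon successful completion of the study, patients will be paid" $50, with a parking voucher if needed. The retest payment is worded differently: "Patients who participate in a retest imaging session will be paid an additional" $150, with no mention of completion. The section neither defines completion of the study nor says what a patient who stops early receives.

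**Endpoint (Section VII, Data Analysis).** "The primary endpoint of this prospective study is the feasibility of multiparametric PET in a general oncology population". Under the primary aim, feasibility is "defined as successful completion of the study imaging component in at least 70% of cases". Success has two parts:

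1. "patient remains on scanner for the full dynamic phase of PET imaging prior to the standard-of-care PET/CT".
2. The scanner software produces valid parametric maps, which needs at least three consecutive whole-body acquisitions without substantial motion between them.

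The aim is described as "evaluating the practicality of acquiring dynamic PET data in the clinic". The plan explains that feasibility has to be established because the long imaging period places added demands on patients.

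**The concern.** Feasibility is in doubt here largely because patients may not tolerate a long acquisition. A payment that appears to depend on finishing acts on that tolerance. It bears on the first part of the endpoint directly, and on the second part to the extent that valid maps depend on lying still.

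Two things are at stake:

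- **Interpretation.** The rate is meant to speak to practicality in the clinic. That routine patients would not be paid to finish is an inference, but a natural one, since the documents describe the $50 only as study compensation. If the payment retains some patients who would otherwise leave, the observed rate overstates the rate without payment.
- **Participants.** Section VIII, under PET/CT imaging risks, accepts that lying still for a long time may be uncomfortable. A payment that seems to be lost on stopping gives such a patient a reason to continue.

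**Working it through.** **Step 1. Do the two conditions overlap?**

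| Event | Payment condition (Section V) | Endpoint (Section VII) |
|---|---|---|
| Patient leaves during the dynamic phase | Study not completed | Failure on part 1 |
| Patient stays, but the software cannot produce maps | Not stated | Failure on part 2 |
| Patient finishes the dynamic phase with valid maps, but leaves before the roughly 20 minutes of imaging after the clinical scan (Section VI, step 10) | Study arguably not completed | Success |

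The first row falls outside completion on any reading of either section. The other two rows show that the conditions are not identical.

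**Step 2. Reproduce the plan's interval.** Inputs from Section VII: n = 75, x = 61, exact 95% interval. The Clopper-Pearson limits are

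- lower = Beta quantile(0.025; x, n − x + 1) = Beta quantile(0.025; 61, 15) = 70.67%
- upper = Beta quantile(0.975; x + 1, n − x) = Beta quantile(0.975; 62, 14) = 89.40%

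These round to the stated 71–89%, so the plan's figure is right. For x = 60 the lower limit is 69.17%. Hence 61 is the smallest count whose lower limit reaches 70%. I take that as the decision rule, because it is the reasoning in the sample size paragraph.

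**Step 3. Effect of an assumed lift.** The documents give no unpaid completion rate (p) and no payment effect (d). Both are assumptions, shown as a range. The chance of meeting the rule is

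P(X ≥ 61), with X ~ Binomial(75, p + d).

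The case of interest is p below 70%, because only there would a declaration of feasibility be wrong under the plan's own definition.

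| Assumed unpaid rate | d = 0 | d = 2 points | d = 5 points | d = 8 points |
|---|---|---|---|---|
| 65% | 0.15% | 0.4% (at 67%) | 1.9% (at 70%) | 6.4% (at 73%) |
| 69% | 1.2% | 2.9% (at 71%) | 9.1% (at 74%) | 22.9% (at 77%) |

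**Step 4. Cost of paying everyone who starts.** In the plan's illustration 75 − 61 = 14 patients do not complete, and 14 × $50 = $700. This is an upper figure for that illustration, because it supposes that none of the 14 would be paid under the present wording.

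**The case against.** The case against has real force on several points.

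- **Non-completers may be paid.** Section V never says that they receive nothing, and its first sentence ties compensation to participation. Consent pages were removed from the text available here and may deal with early stopping. This stands, so it cannot be asserted that patients are paid only if they finish. Even so, the one sentence that sets a condition for the $50 names successful completion, and the retest sentence beside it does not.
- **The two completions differ.** This also stands. Payment refers to the whole study and the endpoint to the dynamic phase plus maps. Map generation is partly technical and outside the patient's control. This limits the possible effect but does not remove it, since success needs both parts.
- **No effect is documented.** Correct. Whether $50 changes the behaviour of oncology patients who are already attending for a clinical scan is unknown.

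A reader might infer more than this, in three ways that the documents do not support. The first is that the completion rate is biased upward as a matter of fact, which nothing in the plan establishes. The second is that the result lies close to the threshold. There is no result: 61 of 75 is an illustration, and the step between 60 and 61 exists in any rule based on an exact limit, whatever patients are paid. The third starts from an unpaid rate of 75%, where a lift of 8 points takes the chance of meeting the rule from 12.7% to 71.3%. But 75% already meets the 70% definition, so that scenario shows a true conclusion reached more often and no false one.

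**Conclusion.** The point holds as a plausible and avoidable incentive, not as a demonstrated bias. The payment condition and the primary endpoint share one event, staying on the scanner through the dynamic phase, and the wording of Section V favours it. If the unpaid rate is just below the threshold and the lift is as large as 8 points, the chance of wrongly declaring feasibility could reach about 23%. With an unpaid rate of 65% or a small lift, it stays in low single figures. These sizes rest wholly on the assumed unpaid rates and lifts, and on reading the rule as a lower confidence limit of at least 70%. The sample size and the 71–89% interval are unaffected. The change is worth making because it is cheap, removes the incentive, and takes pressure off uncomfortable patients.

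**What to change.** Reword the Section V sentence so that the $50, and the parking voucher where needed, go to every patient who starts the research imaging, whether or not it is completed. This also settles what is paid on early stopping. In Section VII and in the report, state that completion was measured in compensated participants and may not carry over unchanged to routine practice. The statement is needed even after the rewording, and more so for any patients already enrolled under the present terms.

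Cost: a short amendment and up to about $700 plus any parking, if 14 of 75 do not complete and would otherwise go unpaid. No change to the sample size, endpoint definition or analysis is needed.

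### Section VII defines feasibility as an observed completion share of at least 70% (53 of 75 suffices), while its sample size rests on an exact lower confidence limit of at least 70% (61 of 75), never written as the rule

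*Combined protocol and SAP*

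**What the plan says.** Section VII (Data Analysis) uses the word feasible in two places, with two different standards.

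- **Opening (sample size) paragraph.** It fixes the size: "A total of 75 subjects will be recruited for the multiparametric PET portion of the study". It then gives an example: "If we observe a successful completion rate of 81.3% (i.e., 61 of 75 subjects"), for which "the exact 95% confidence interval for that proportion and sample size would be 71-89"%. From this it reasons: "The lower limit of this confidence interval will effectively indicate that the true successful completion rate is highly likely to be" at least 70% "and that multiparametric PET is feasible in a general oncology population".
- **Primary aim paragraph.** It gives the only sentence worded as a definition: feasibility "will be defined as successful completion of the study imaging component in at least 70% of cases". It then states what counts as successful completion for one patient, but attaches no interval, test or minimum count to the 70%.

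No other section supplies a decision rule for the primary endpoint. The documents give no expected completion rate, significance level or power beyond the 61 of 75 example.

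**The concern.** A share of cases is most naturally read as an observed proportion. On that reading the primary endpoint is met as soon as the observed rate reaches 70%, however wide the interval around it. The sample size paragraph asks for more: evidence that the true rate is at least 70%. A result between the two bars could be reported as feasible under the definition, although the plan's own basis for that word would not hold.

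This is the study's only primary verdict. An analyst with 57 of 75 successes could cite the definition and report feasibility without departing from the plan; another could cite the sample size paragraph and report that feasibility was not shown. The interval that would let a reader judge the label appears only in the sample size example, and the Primary aim paragraph does not commit to reporting it.

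**Working it through.** **Inputs, all from Section VII:** n = 75; benchmark 70%; exact 95% confidence interval; example 61 of 75, interval 71–89%. True completion rates below are assumptions, shown as a range.

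**1. Reproduce the plan's interval.** For x successes of n, the two-sided exact (Clopper-Pearson) limits are

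L = Beta quantile at 0.025 with parameters (x, n − x + 1); U = Beta quantile at 0.975 with parameters (x + 1, n − x).

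For x = 61, n = 75: 61/75 = 81.3%, L = 70.7%, U = 89.4%. This rounds to the stated 71–89%, so the plan's figure is correct and is a two-sided interval.

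**2. Find the smallest passing count under each reading.** The last column is the one-sided exact p-value against 70%, P(X ≥ x) with X ~ Binomial(75, 0.70).

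| Successes of 75 | Observed | Exact 95% CI | Observed share ≥ 70%? | Lower limit ≥ 70%? | One-sided p |
|---|---|---|---|---|---|
| 52 | 69.3% | 57.6–79.5% | no | no | 0.605 |
| 53 | 70.7% | 59.0–80.6% | **yes** | no | 0.507 |
| 60 | 80.0% | 69.2–88.4% | yes | no | 0.035 |
| 61 | 81.3% | 70.7–89.4% | yes | **yes** | 0.019 |

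The literal bar is 53 and the lower-limit bar is 61. The readings disagree for the eight counts from 53 to 60. That the plan's example falls exactly on the lower-limit bar is good evidence that 61 was meant as the minimum passing count.

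**3. Chance of declaring feasibility under each reading.** With X ~ Binomial(75, p), the literal rule passes with probability P(X ≥ 53) and the lower-limit rule with P(X ≥ 61). The difference is the chance that they disagree.

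| Assumed true rate p | Literal, P(X ≥ 53) | Lower limit, P(X ≥ 61) | Disagree, P(53 ≤ X ≤ 60) |
|---|---|---|---|
| 60% | 3.7% | <0.1% | 3.7% |
| 65% | 18.3% | 0.15% | 18% |
| 70% | 50.7% | 1.9% | 49% |
| 75% | 84.2% | 12.7% | 71% |
| 80% | 98.1% | 45.4% | 53% |
| 81.3% | 99.1% | 56.8% | 42% |
| 85% | >99.9% | 85.3% | 15% |
| 90% | >99.9% | 99.3% | 0.7% |

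Disagreement is more likely than not only for true rates from 70.2% to 80.3%, with a maximum of 71.7% at 75.5%.

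**4. Does the example alone fix the cutoff?** No. At 60 of 75 the two-sided exact lower limit is 69.2% and fails, but a one-sided 95% exact limit (70.9%) or a Wald interval (lower limit 70.9%) would pass. The count also moves with the number analysed: 57 of 70, 59 of 72, 60 of 74, 65 of 80.

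**The case against.** The strongest reply is that the two paragraphs can be read together without conflict. The definition says what feasibility means, a rate of at least 70%; the paragraph just above says what evidence supports it, an exact 95% lower limit at that level. The interval type, the confidence level, the benchmark and the minimum count are all on the page, and only an explicit statement that this is the rule is missing. This is probably what was intended, and the choice of 61 supports it. It does not remove the gap. The sentence that carries the definition speaks of a share of cases and refers to no interval, and the rule a reader must infer is stated only for one hypothetical result.

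A second reply concerns size. The chance of landing between 53 and 60 measures how often the readings differ, not how often a wrong conclusion is drawn. At true rates of 75–80% the target is met in truth, so calling the procedure feasible would be correct, though not demonstrated at the stated confidence. This stands. The clearest evidence of harm is therefore at rates below 70%, such as 18.3% against 0.15% at 65%.

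Third, this is a single-group imaging feasibility study, and a reader given the count and denominator can compute the interval. That also stands: the label is at risk, not the estimate.

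**Conclusion.** The concern holds. As written, the definition of the primary endpoint is met at 53 of 75, where the exact interval extends down to 59.0%, while the plan's justification for its sample size requires 61 of 75. For 53 to 60 successes the section supports opposite verdicts. Taken literally, the definition would declare feasibility about half the time at a true rate of exactly 70%, and about one time in five or six at 65%, below the study's own threshold.

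The counts and intervals follow from the plan's figures and assume 75 subjects analysed, one result each. The probabilities also depend on assumed true rates: disagreement is rare at 60% or 90% and common between about 70% and 80%. The stated 71–89% interval is right. The defect is in the decision rule and should be fixed before results are seen.

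**What to change.** Add one rule to Section VII, for example: *Feasibility will be concluded if the lower limit of the exact two-sided 95% confidence interval for the per-subject completion rate is at least 70% (at least 61 successes if 75 subjects are analysed; the count will be recomputed if the number analysed differs). Otherwise the rate and its interval will be reported with the statement that a rate of at least 70% was not demonstrated.*

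If the sponsor prefers the observed share as the criterion, the plan should say so and drop the claim that the true rate is highly likely to reach 70%.

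A minor wording point: count subjects, not cases, in the definition. The note in Section III says "Patients scheduled to undergo multiple PET/CT imaging procedures will be eligible to have dynamic imaging performed during each of these procedures", and extra sessions should not enter the primary denominator by accident. No effect of this on the result is shown.

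The change needs no new patients. Its cost is a harder bar: 61 of 75 is met with probability 45% at a true rate of 80%, 57% at 81.3% and 85% at 85%. An 80% chance of meeting it needs a true rate of about 84.2%, and a 90% chance about 85.9%. The literal bar of 53 is met 98% of the time at a true rate of 80%, but it does not support the claim the plan makes.
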